4.6. Randomization and procedure for breaking the code

A randomization code for allocating the study treatments will be prepared by a masked biostatistician not connected with the study.

At the initiation of study related procedures, every potential subject is assigned a **Screening number** in numerical order. Once a subject is qualified for the study (Qualification/Baseline Visit) the subject is assigned a **randomization number** in the order provided by the biostatistician.

The study medications will be masked to both Investigator and study subjects, as well as Ocuphire. Treatment assignments will be masked to the Investigator, Ocuphire, and the subjects. Only in case of medical emergency or occurrence of serious adverse events (SAE) will the randomization code be unmasked by the study pharmacist and made available to the Investigator, Ocuphire, and/or other personnel involved in the monitoring or conduct of this study.

4.7. Collection of data

The source documentation for all data collected in the study will be maintained by the investigator in the subject files at the study site. All original data collected during this trial is to be recorded on paper case report forms (CRFs) and then electronically entered into the database following study completion. The paper CRF is considered to be the source documentation for this study.

4.8. Completed subject

A completed subject is defined as one who completes all planned dosing and procedures through Day 22.

4.9. Non-completing subject

A non-completing subject is defined as one who exits the study by their own volition or at the discretion of the Investigator and/or the Medical Monitor prior to completing all of the study procedures required in this protocol. Any subject may decide to voluntarily withdraw from the study at any time without prejudice.

4.9.1. Study medication discontinuation

The study medication may be discontinued for the following reasons:

- **Adverse Events:** Adverse events including clinically significant laboratory abnormalities and intercurrent diseases reported by the subject or observed by the investigator with documentation on the case report form (CRF).
- **Death:** If a subject dies, the adverse event that caused the death should be documented on the CRF and be noted as serious and fatal.
- **Disallowed concurrent medication:** Any medication not allowed by the protocol would be a protocol violation.
- **Lack of efficacy:** A subject may elect to discontinue participation in the study for a perceived lack of efficacy.
- **Investigator decision:** A subject may be discontinued for reasons other than those bulleted previously if the investigator thinks it is not in the best interest of the subject to continue.
- **Other:** If there is any other reason for subject discontinuation this should be noted on the CRF.

The reason for premature study medication discontinuation should be entered onto the appropriate CRF. In the event that discontinuation of study medication occurs after a completed single dose, the Investigator will make every attempt to complete all subsequent safety assessments at Day 15 and Day 22.

4.9.2. Reasons for Withdrawal from Study

- Subject withdraws consent.
- Subject is non-compliant, e.g. missed three or more daily use of medication.
- Subject is lost to follow-up.
- Subject withdraws for other reason.

4.9.3. Entire study terminated

The entire study may be terminated by Investigators or the Sponsor. Prompt, written notice of reasonable cause to the other party (Sponsor or Investigators, respectively) is required. Prompt notice to the IRB and to regulatory authorities is also required.

4.9.4. Actions after discontinuation

All subjects who discontinue study medication due to a report of an AE **must** be followed-up and provided appropriate medical care until their signs and symptoms have remitted or stabilized or until abnormal laboratory findings have returned to acceptable or pre-study limits.

For any subject who chooses to withdraw consent or who is non-compliant, every possible effort should be made by the Investigator to assure there is a final visit that includes all examinations listed for the Follow-up Visit.

4.10. Completed study

The study is completed when all randomized subjects have completed the study, all CRFs have been completed, and all CRF data entered into the database. Final DB lock will occur after the last randomized subject completes, all data has been entered and all queries resolved.

4.11. Procedure after the completion of the study

When the study is completed, Oculos will provide Ocuphire and the IRB with a brief (i.e., one to three pages) report, containing a description of the study, the number of subjects enrolled, the number of subjects completed the number of subjects who dropped out and why, efficacy findings and adverse events.

5. SUBJECT INCLUSION AND EXCLUSION CRITERIA

Subjects may qualify in either eye. The eye with the higher IOP at the Qualification/Baseline Visit at 8AM is designated as the study eye. In the case where both eyes have the same IOP, the study eye will be the RIGHT eye. See Section 9 for more information on statistical analysis. ALL TREATMENTS WILL BE ADMINISTERED TO BOTH EYES (OU).

5.1. *Subject inclusion criteria*

1. 18 years of age or greater.
2. Diagnosis of OAG or OHT. The diagnosis of OHT must be in BOTH eyes. For OAG it can be in either eye and OHT in the fellow eye. A reported history of untreated OHT with IOP ≥ 22 mmHg and ≤ 30 mmHg is preferred.
3. Untreated or treated OAG/OHT with 2 or fewer ocular hypotensive medications.
4. Untreated (post-washout) mean IOP ≥ 22 mmHg and ≤ 30 mmHg in the study eye at the Qualification Visit (8AM).
5. Corrected visual acuity in each eye $+1.0$ logMAR or better by Early Treatment Diabetic Retinopathy Study (ETDRS) in each eye (equivalent to 20/200 or better).
6. Otherwise healthy and well controlled subjects.
7. Able and willing to give signed informed consent and follow study instructions.
8. Able to self-administer study medication or to have study medication administered by a caregiver throughout the study period.

5.2 *Subject exclusion criteria*

Excluded from the study will be individuals with the following characteristics in either eye:

Ophthalmic:

1. Closed or very narrow angles (Grade 0-1, Shaffer¹) or angles that the investigator judges as occludable and/or with evidence of peripheral anterior synechiae (PAS) ≥ 180 degrees by gonioscopy within 6 months prior to Screening Visit in either eye.
2. Glaucoma: pseudo-exfoliation or pigment dispersion component, history of angle closure, or narrow angles. Note: Previous laser peripheral iridotomy is NOT allowed.
3. Known hypersensitivity to any α -adrenoceptor antagonists.
4. Previous laser and/or non-laser glaucoma surgery or procedure in either eye.
5. Refractive surgery in either eye (i.e. radial keratotomy, PRK, LASIK, corneal cross linking).
6. Ocular trauma in either eye within the 6 months prior to Screening, or ocular surgery or non-refractive laser treatment within the 3 months prior to Screening.
7. Recent or current evidence of ocular infection or inflammation in either eye. Current evidence of clinically significant blepharitis, conjunctivitis, or a history of herpes simplex or herpes zoster keratitis at Screening in either eye.

8. Ocular medication in either eye of any kind within 30 days of Screening, with the exception of a) ocular hypotensive medications (which must be washed out according to the provided schedule), b) lid scrubs (which can be used prior to Screening but cannot be used after Screening) or c) lubricating drops for dry eye (preservative-free artificial tears), which may be used throughout the study.
9. Clinically significant ocular disease in either eye as deemed by the investigator (i.e., corneal edema, uveitis, severe keratoconjunctivitis sicca) that might interfere with the study, including glaucomatous damage so severe that washout of ocular hypotensive medications for 1 month is not judged safe (i.e., cup-to-disc ratio > 0.8, severe visual field defect).
10. History of diabetic retinopathy.
11. Contact lens wear within 3 days prior to and for the duration of the study.
12. Central corneal thickness in either >600 μm at Screening.
13. Any abnormality in either eye preventing reliable applanation tonometry (e.g. central corneal scarring).

Systemic:

1. Known hypersensitivity or contraindication to α - and/or β -adrenoceptor antagonists (i.e. chronic obstructive pulmonary disease or bronchial asthma; abnormally low blood pressure or heart rate; second or third degree heart block or CHF; severe diabetes).
2. Clinically significant systemic disease (i.e., uncontrolled diabetes, myasthenia gravis, cancer, hepatic, renal, endocrine or cardiovascular disorders) that might interfere with the study.
3. Participation in any investigational study within 30 days prior to Screening.
4. Use of any topical or systemic adrenergic or cholinergic drugs up to 30 days prior to Screening, or during the study unless the drug, dose and regimen has been consistent for the 30 days prior to Screening.
5. Changes in systemic medication that could have an effect on IOP within 30 days prior to Screening or anticipated during the study.
6. Women of childbearing potential who are pregnant, nursing, planning a pregnancy, or not using a medically acceptable form of birth control. An adult woman is considered to be of childbearing potential unless she is 1 year postmenopausal or 3 months post-surgical sterilization. All females of childbearing potential must have a negative urine pregnancy test result at the Screening examination and must intend to not become pregnant during the study.
7. Resting heart rate (HR) outside the normal range (50-110 beats per minute at the Screening or Qualification Visit. HR may be repeated **once only** if outside the specified range following at least a 5 minute rest period in the sitting position.
8. Hypertension with resting diastolic blood pressure (BP) > 105 mmHg or systolic BP > 160 mmHg at the Screening or Qualification Visit. BP may be repeated **once only**

if outside the specified range following at least a 5 minute rest period in the sitting position.

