Exclusion Criteria	Ophthalmic: 
1. Closed or very narrow angles (Grade 0-1, Shaffer) or angles that the investigator judges as occludable and/or with evidence of peripheral anterior synechiae (PAS) \geq 180 degrees by gonioscopy within 6 months prior to Screening Visit in either eye.2. Glaucoma: pseudo-exfoliation or pigment dispersion component, history of angle closure or narrow angles. Note: Previous laser peripheral iridotomy is NOT allowed.3. Known hypersensitivity to any α-adrenoceptor antagonists.4. Previous laser and/or non-laser glaucoma surgery or procedure in either eye.5. Refractive surgery in either eye (i.e. radial keratotomy, PRK, LASIK, corneal cross linking).6. Ocular trauma in either eye within the 6 months prior to Screening, or ocular surgery or non-refractive laser treatment within the 3 months prior to Screening.7. Recent or current evidence of ocular infection or inflammation in either eye. Current evidence of clinically significant blepharitis, conjunctivitis, or a history of herpes simplex or herpes zoster keratitis at Screening in either eye.8. Ocular medication in either eye of any kind within 30 days of Screening, with the exception of a) ocular hypotensive medications (which must be washed out according to the provided schedule), b) lid scrubs (which can be used prior to Screening but cannot be used after Screening) or c) lubricating drops for dry eye (preservative-free artificial tears), which can be used throughout the study.9. Clinically significant ocular disease in either eye as deemed by the investigator (i.e., corneal edema, uveitis, severe keratoconjunctivitis sicca) that might interfere with the study, including glaucomatous damage so severe that washout of ocular hypotensive medications for 1 month is not judged safe (i.e., cup-to-disc ratio $>$ 0.8, severe visual field defect).10. History of diabetic retinopathy.
---------------------------	--

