4.5. Expected duration of subject participation

The total length of subject participation is approximately 7-8 weeks with six clinic visits and one telephone call summarized below:

- Screening Visit (1 day).
- Washout Visit/period (as necessary) (4-5 weeks with safety check visit at 2 weeks).
- Qualification/Baseline Visit (1 day).
- Treatment-study Visit Day 8 (1 week).
- Treatment-study Visit Day 15 (1 week).
- Follow-up clinic Visit on Day 16 (1 day).
- Follow-up telephone call on Day 22 (1 week).

The execution of the entire study (first subject screen through last randomized subject completed) is expected to be approximately 6 months.

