7.2.2. Washout Period

After Screening, study participants will be required to refrain from administration of any glaucoma drugs for at least 28 days and no more than 35 days prior to the Qualification/Baseline Visit. The washout subjects will be brought back in approximately two weeks after the Screening Visit for an IOP safety check. In the judgement of the investigator, if there is any risk to the eye(s) of the subject, or if the mean IOP in either eye is >30 mmHg, then an appropriate rescue or prior medication will be administered, and the subject will be considered a screen failure. Adverse events occurring during the washout period and a review of concomitant medications will also be assessed at this visit.

Unmedicated subjects who meet the inclusion/exclusion criteria after screening do not have a washout period. These subjects may return the following day or up to 35 days later for their Qualification/Baseline Visit.

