7.2.3. Qualification Visit/Baseline (Day 1)

At the Qualification/Baseline Visit, the subject will be asked how do his/her eyes feel, and if there have been any changes in their medical condition, or concomitant medications since their last visit. Any adverse changes in the condition of the subject at this visit are recorded in the Medical/Ophthalmic History CRF.

At the Qualification/Baseline Visit:

- Females of childbearing potential will take a urine pregnancy test at 8AM.
- Review of concomitant medications at 8AM.
- IOP measurements using a [REDACTED] at the Baseline visit and both Treatment-study visits will be done at 8AM, 10AM and 4PM. All IOP measurements have a window of ± 15 minutes with at least 2 hours between the 8AM and 10AM assessments. IOP will be measured twice in both eyes at each timepoint. The mean value at each timepoint for the study eye will be used in efficacy assessments. If the difference in the two IOP measurements is >5 mmHg, a third measurement will be obtained, and the three values averaged.
- Pupil diameter, using a [REDACTED], near visual acuity using a standard chart held at 14 inches and distance visual acuity with ETDRS are measured at 8AM.
- Resting HR and BP are measured at 8AM and 4PM. Blood pressure, using the same arm, same cuff size appropriate for arm circumference throughout the study, and heart rate should be measured after at least 3 minutes rest in the sitting position. If HR or BP are outside the normal range (see Exclusion Criteria – Systemic #7 and #8), they may be repeated only once following at least a 5 minute rest period in the sitting position.
- Eye redness (conjunctival hyperemia) visually checked at 8AM, 10AM and 4PM using [REDACTED]
- Adverse events will be reviewed at each timepoint.

To continue in the study, the subject must have a mean IOP ≥ 22 mmHg at 8AM and ≥ 19 mmHg at 10AM and 4PM in the study eye **after the washout period** (if required) at the Qualification Visit (8AM).

Subjects may qualify in either eye. The eye with the higher IOP at the Qualification Visit at 8AM is designated as the study eye for the efficacy endpoints. In the case where both eyes have the same IOP, the study eye will be the RIGHT eye. See Section 9 for more information on statistical analysis. ALL TREATMENTS WILL BE ADMINISTERED TO BOTH EYES (O.U.).

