If the subject meets all of the inclusion criteria and none of the exclusion criteria, including all three timepoint IOP measurements, this qualification visit becomes the Baseline Visit, a subject number is assigned, and he/she is randomized into the study.

Site personnel will demonstrate the proper instillation technique to the subject at the Qualification/Baseline Visit (Day 1) and the subject will self-administer a dose of artificial tears at the study site, instilling 1 drop in each eye from the unit-dose bottle (Note: if a drop is not instilled into the eye, the subject should wait approximately 10-15 seconds and administer a second drop). The subject should be in a seated position and should tilt his or her head backward for administration of the study medication. The bottle of study medication should be held at an almost vertical position above the eye while the lower eyelid is pulled down gently, and 1 drop is placed into the conjunctival cul-de-sac. The tip of the bottle should not touch the eye. After a drop is instilled in each eye, the subject should keep the eyes gently closed for approximately 30 seconds. After successful instillation of the drop in each eye, the subject should carefully empty any remaining contents as directed.

The subject is given their study medication dropper bottles, and with instructions when to administer the eye drop (8PM to 10PM), and when to return to the clinic.

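### Exclusion 9 tests glaucomatous damage against the 1-month washout only and leaves out the further 20-22 days to the Day 22 call when own medication is still withheld

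*Protocol*

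**What the plan says.** Exclusion 9 opens broadly: "Clinically significant ocular disease in either eye as deemed by the investigator", where that disease might interfere with the study. It then lists, as an included case, damage from glaucoma so severe that "washout of ocular hypotensive medications for 1 month is not judged safe", and illustrates this with a cup-to-disc ratio above 0.8 and a severe field defect. The Synopsis and section 5.2 carry the same clause.

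Protocol 7.2.2 has treated subjects stop all glaucoma drugs "for at least 28 days and no more than 35 days prior to the Qualification/Baseline Visit". They are then randomized 1:1 to Nyxol or vehicle, dosed on Days 1 to 14 (sections 4.2 and 6). On Day 15, and again on Day 16, they are told not to restart their own medication until the Day 22 call is done (sections 7.2.5 and 7.2.6). They are advised to restart at that call (section 7.2.7).

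Eligibility is checked again before randomization (section 7.2.3): "If the subject meets all of the inclusion criteria and none of the exclusion criteria", the Qualification Visit becomes Baseline.

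**The concern.** The clause asks the investigator whether the optic nerve and visual field can tolerate a period without pressure-lowering treatment, but the period it names ends at Baseline. The protocol withholds the subject's own medication for about three weeks more, and a subject on vehicle has no active pressure-lowering drug during that time.

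The re-check at Qualification makes the gap plainer. By then the washout is complete, so the glaucoma clause, read as written, asks about a period already past and not about the weeks still to come.

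What is at stake is subject protection at the margin. A treated eye that an investigator would accept for 4-5 weeks off therapy, but not for 7-8, is not prompted for by the text.

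**Working it through.** **Inputs**

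- Washout before Qualification/Baseline: 28 to 35 days (Protocol 7.2.2).
- Qualification/Baseline is Day 1 (Protocol 7.2.3).
- Own medication resumes at the Day 22 call (Protocol 7.2.5 to 7.2.7).
- The Day 15 visit may be one day early or late, and the Day 22 call moves with it (Protocol 7.2.9).
- Dosing covers 14 days (Protocol 4.2).

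**Step 1: reproduce the plan's own figure.** Protocol 4.5 states: "The total length of subject participation is approximately 7-8 weeks". Washout plus the interval from Day 1 to Day 22 gives:

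- shortest: 28 + (22 − 1) = 28 + 21 = 49 days; 49/7 = 7.0 weeks
- longest: 35 + 21 = 56 days; 56/7 = 8.0 weeks

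This matches. For a treated subject, the stated participation time is also the time off own medication.

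**Step 2: add the visit window.**

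- shortest: 28 + 20 = 48 days; 48/7 = 6.86 weeks
- longest: 35 + 22 = 57 days; 57/7 = 8.14 weeks

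**Step 3: compare with the period the clause names.** The part left out is 20, 21 or 22 days, all of it still ahead at the Qualification decision. Total time off own medication as a multiple of the washout:

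- nominal: 56/35 = 1.60 to 49/28 = 1.75
- with the window: 55/35 = 1.57 to 50/28 = 1.79

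**Step 4: separate the arms.** On vehicle, the whole 49-56 days passes without an active pressure-lowering drug. On Nyxol, 14 of those days are dosing days. That leaves 49 − 14 = 35 to 56 − 14 = 42 days with neither own drug nor study drug, which is 7 days more than the washout (21 − 14).

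**Step 5: sensitivity to one ambiguity.** Section 7.2.7 also describes the call as a week after the last dose. Counted from Day 14 this is Day 21, giving 28 + 20 = 48 to 35 + 20 = 55 days on the nominal schedule. The protocol names Day 22 elsewhere, and one day does not alter the comparison.

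**Not derivable.** The documents give no distribution of disc or field damage, so the number of subjects whose eligibility would change cannot be computed.

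**The case against.** The strongest reply is that nothing in the clause is false. Washout in this protocol means the 28-35 days before Qualification, and one month describes that correctly. The investigator also has the rest of the protocol, including the 7-8 week duration and the instruction to withhold own drops until Day 22. The head wording of exclusion 9 already lets an eye be excluded on wider grounds, and the examples exclude the same eyes whatever the duration. All of this stands. It confines the point to borderline eyes and rules out calling the one-month figure an error.

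A reader might go further and infer that subjects are unprotected after Baseline. The documents do not support that:

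- The check about two weeks into washout leads to rescue and screen failure for any perceived risk to the eye, or for mean IOP above 30 mmHg in either eye.
- IOP is re-checked before randomization: "To continue in the study, the subject must have a mean IOP" in the required range. The 8AM ceiling of 30 mmHg applies to the higher-pressure eye and so bounds both.
- IOP is measured on Days 8, 15 and 16, and unscheduled visits are allowed.
- Study drug may be stopped "if the investigator thinks it is not in the best interest of the subject to continue".

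These safeguards have limits. The 30 mmHg rescue rule is stated for the washout, the visible text gives no numeric threshold after randomization, and no IOP measurement is scheduled between Day 16 and the Day 22 telephone call. None of them changes the period that exclusion 9 asks the investigator to weigh beforehand.

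**Conclusion.** The point holds as a minor one. The clause labels the washout correctly but, as a safety test, leaves out 20-22 of the 48-57 days for which previously treated subjects are without their own medication (21 of 49-56 on the nominal schedule). The figures rest only on the protocol's schedule and on subjects following the instruction not to restart before the call. The number of subjects who would be judged differently is unknown and may be zero.

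Two stronger readings should be resisted. One is that 7-8 weeks off treatment is unsafe, or that the washout is too long; the documents contain no evidence on either. The other is that the efficacy result is compromised; the primary endpoint, its ANCOVA and the analysis sets do not depend on this clause. Nor is every subject untreated throughout, since the Nyxol arm receives study drug on 14 of the days.

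**What to change.** In exclusion 9, in both the Synopsis and section 5.2, replace "washout of ocular hypotensive medications for 1 month is not judged safe" with:

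> being without ocular hypotensive medication for the whole study period (up to about 8 weeks from start of any washout through the Day 22 call), possibly while on vehicle, is not judged safe

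Do not add a limiter such as *for subjects on ocular hypotensive medication*. Untreated subjects are eligible under inclusion 3, and a limiter would detach the disc and field examples from them. Read literally, it would also stop the clause applying at Qualification to subjects who have already washed out.

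Leave the examples, the washout length and the visit schedule as they are. The cost is one clause in two places, with no change to procedures, sample size or analysis. The downside is that a few borderline subjects may be excluded.
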